10.8 Treatment-emergent Adverse Event (TEAE)

For subjects in Cohort 1, AEs will be considered treatment-emergent to Period 1 if they have missing or partial start dates for which it cannot be determined whether the AE started before or after the Period 1 or Period 2 first dose of study medication.

For subjects in Cohort 2, AEs will be considered treatment-emergent to Period 2 if they have missing or partial start dates for which it cannot be determined whether the AE started before or after the Period 2 first dose of study medication.

As there will be no interruption of study drug treatment between Period 2, Period 3 and LTE, those 3 periods will be considered only one period and referred to Period 2 in the below definitions.

Period 1

Treatment-emergent AEs (TEAEs) are defined as any AE(s) or SAE(s), regardless of relationship to study drug, that have an onset or worsening in severity on or after the first dose of study drug until 30 days after Period 1 last dose of treatment date.

Period 2

TEAEs are defined as any AE(s) or SAE(s), regardless of relationship to study drug, that have an onset or worsening in severity on or after the Period 2 first dose of study drug until 30 days after the last dose of treatment in the study.

Each AE is mapped to a Period based on their start date, using the rules defined in Table 2. If the start date is partial, determination of the Period will based on the imputed start date (see Section 10.11 for details). If the date is entirely missing, the AE will be assigned to Period 1 for subjects in Cohort 1 and to Period 2 for subjects in Cohort 2.

Cohort	Analysis Period	Start of the Period	End of the Period
	1*	Data of ICE	If the subject continued in Period 2: last dose in Period 1 + 30 days.
	1.	Date of ICF	If the subject did not continue in Period 2: all AEs are assigned to Period 1.
1	2	Date of Outpatient	If the subject continued in Period 3: last dose in Period 2.
	2	Admission Visit	If the subject did not continue in Period 3: Date of completion/discontinuation of the study
	3	Last dose date in Period 2 + 1 day	If the subject continued in LTE: last dose in Period 3.
			If the subject did not continue in LTE: Date of completion/discontinuation of the study
	LTE	Last dose date in Period 3 + 1 day	Date of completion/discontinuation of the study
	2		If the subject continued in Period 3: last dose in Period 2.
2	2	Date of ICF	If the subject did not continue in Period 3: all AEs are assigned to Period 2.
	_	Last dose date in	If the subject continued in LTE: last dose in Period 3.
	3	Period 2 + 1 day	If the subject did not continue in LTE: Date of completion/discontinuation of the study
	LTE	Last dose date in Period 3 + 1 day	Date of completion/discontinuation of the study

Table 2: Mapping Rules of AE to Each Period

- * AEs that occurred between the last dose in Period 1 + 30 days and the date of ICF in Period 2, will be reported in a separate AE listing.
- 10.9 Adverse Events with Outcome of Death

Any AE with an outcome of "fatal" will be considered as AE with an outcome of death.

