For cohort 1, 10-14 days before admission to the NIH CC, participants will undergo outpatient laboratory testing for blood and urine chemistry (Table B). For cohort 2 participants whose screening visit is > 21 days before initiation of study drug, outpatient laboratory testing will be performed 10-14 days prior to admission for blood and urine chemistry.

Results will be reviewed by the NIH investigators.

Participants who complete the screening visit midweek have the option to stay overnight at NIH CC during the intervening days prior to the start of Period 2, Day -1.

All participants will be instructed to stop taking calcitriol on Day -1, the day of admission, but continue their oral calcium supplement regimen until admitted. Magnesium supplements and potassium citrate will be discontinued starting the morning of Day 1. Calcium supplements will be discontinued or decreased starting on Day 1, based on the estimate dietary calcium intake, targeting a combined calcium intake of > 1000 mg/day.

[figure not shown]
Day -1 (Admission): Eligible participants will be admitted to the NIH Clinical Center the day prior to dosing.

**Cohort 1-** Participants in Cohort 1 who complete Period 1 will be scheduled to return for Period 2 after at least 8 weeks and up to 16 weeks (minimum of 8 weeks between Period 1 and 2 for participant participating in both Periods to recover blood volume and hematocrit levels). BID dosing will be individualized based on each participant's prior responses to CLTX-305 (encaleret) during Period 1.

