10.10 Treatment-related Adverse Events

Any AE with a relationship to study treatment of "Related" or missing will be considered a treatmentrelated AE as determined by the Investigator.

- 10.11 Imputation of AE and Concomitant Medication Start and Stop Dates
 - Start Date:
 - If only 'day' is missing, and the month and year are not the same as the month of first dose, then the day will be imputed with 1 (first day of the month). Otherwise, if the month and year are the same as the dose date, the day will be imputed with the day of the first dose of treatment.
 - If 'day' and 'month' are missing, and 'year' is not missing, then the missing month and day will be imputed with the month and day of the first dose date (assuming same 'year').
 - If 'day' and 'month' are missing and 'year' is not missing and is not the same year as first dose date, then the day and month will be imputed with the 1st of January.
 - Stop Date:
 - If only 'day' is missing, the day will be imputed with the last day of the month.
 - If 'day' and 'month' are missing, and 'year' is not missing, then the day and month will be imputed by the 31st of December (or by the date of study discontinuation or completion if earlier than the 31st of December and year is the same as the year of discontinuation).
 - If the stop date is completely missing and the AE/medication is not ongoing, it will be set to the date of study discontinuation or completion.

The imputed dates will be used to assess whether AEs should be considered as treatment-emergent and if medications should be included in the safety summaries as prior or concomitant medications. The original partial dates will be included in data listings.

The duration of AEs will be derived as the AE end date [(including imputation date for incomplete AE end date) – AE onset date (imputed date for incomplete AE onset date) + 1].

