13.6.1 Adverse Events

AE means any untoward medical occurrence associated with the use of an intervention in humans, whether or not considered intervention-related (21 CFR 312.32 (a)).

TEAEs are those which first occur or increase in severity or relationship to study treatment after the first dose of study treatment and not more than 30 days after the last dose of study treatment. All adverse events which change in severity or relationship to study treatment are assigned a new start date and captured as a new record. For subjects in cohort 1, an AE that occurred more than 30 days after the Period 1 last dose of study treatment and before the Period 2 first are not treatment-emergent and are not mapped to a period. Those AEs will be listed separately.

As Period 1 is separate from the other periods, treatment emergence is defined separately for Period 1 and for the other periods; AEs will be mapped to each period for the reporting (see Section 10.8 for more details).

A summary of TEAEs, including the number of events reported, the number and percentage of subjects reporting at least one TEAE regardless of relatedness assessment, the number and percentage of subjects reporting at least one TEAE related to study drug, the number and percentage of subjects discontinuing due to a TEAE, the number and percentage of subjects with at least one serious adverse event, the number and percentage of subjects reporting at least one TEAE of discontinuation of study drug, the number and percentage of subjects reporting at least one TEAE of special interest (symptomatic/asymptomatic hypocalcemia), and the number and percentage of TEAE leading to death (seriousness death) will be presented by period (Period 1, Period 2 + Period 3 and LTE). The same summary will be repeated for AEs.

A breakdown of the number and percentage of subjects with at least one TEAE, categorized by SOC and PT coded according to the MedDRA dictionary, will be presented. Subjects are only counted once within each SOC or PT. The same summary will be repeated for all TEAE related to study drug and for TEAEs leading to discontinuation of study drug.

A summary of events reported, categorized by severity (Mild, Moderate and Severe), will also be provided. Subjects with multiple events within a particular SOC or PT will be counted under the category of their most severe event within that SOC or PT.

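### SAP 10.8 and 10.11 give three different answers for a Cohort 1 adverse event dated only to the month of the Period 2 first dose, and the rule stated first puts it in a period where it can almost never belong

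*SAP*

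**What the plan says.** Three rules in the SAP bear on a Cohort 1 event without a complete start date.

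- **Opening rule of 10.8.** It states that "AEs will be considered treatment-emergent to Period 1 if they have missing or partial start dates" and it cannot be determined "whether the AE started before or after the Period 1 or Period 2 first dose of study medication".
- **Mapping rule, later in 10.8.** "If the start date is partial, determination of the Period will based on the imputed start date", as set out in 10.11. For a wholly missing date: "If the date is entirely missing, the AE will be assigned to Period 1 for subjects in Cohort 1".
- **Imputation rule, 10.11.** The condition "If only 'day' is missing, and the month and year are not the same as the month of first dose" leads to the first of the month. When the month and year do match, "the day will be imputed with the day of the first dose of treatment". Section 10.11 also says that imputed dates decide treatment emergence, so it answers the same question as the opening rule of 10.8.

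The Period 1 TEAE window closes 30 days after the last Period 1 dose (10.8). Cohort 1 events after that and before the Period 2 first dose "are not treatment-emergent and are not mapped to a period" (13.6.1); they appear in a separate listing. Protocol 8.2.2 brings Cohort 1 back for Period 2 "after at least 8 weeks and up to 16 weeks".

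**The concern.** Cohort 1 participants have two first doses, about two to four months apart. When the known part of a start date spans the second one, the opening rule and the imputation rule both apply, and neither is ranked above the other. Section 10.11 does not say which first dose it means. Two programmers following the text could put the same record in Period 1, in Period 2, or in no TEAE table at all.

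AE and SAE counts are a primary endpoint for Periods 1 to 3 (SAP 9.0), and 13.6.1 tabulates TEAEs by period: Period 1, Periods 2 and 3 together, and the LTE. The opening rule keeps the event as a TEAE but in the wrong period. The gap outcome removes from the TEAE tables an event that may have begun on drug.

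**Working it through.** The plan gives no figure on this point, so there is none to reproduce. The check applies each rule literally to one case: a Cohort 1 AE for which only the month and year are known, and these are the month and year of the Period 2 first dose.

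**Inputs.** Period 1 has 5 dosing days (SAP 8.0), so the last dose is on Day 5. The Period 1 window ends at last dose + 30 days (SAP 10.8). The interval is 8 to 16 weeks, that is 56 to 112 days (Protocol 8.2.2). I assume that the interval runs from the last Period 1 dose to Period 2 Day 1, and that admission is on Day -1.

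**Worked example (assumed dates, 70-day interval).** Period 1 dosing runs 11 to 15 January 2021, so the window closes on 14 February. Period 2 admission is 25 March and the first dose 26 March. The AE is recorded as March 2021.

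| Rule | Date used | Result |
|---|---|---|
| 10.8 opening rule | none | Period 1 TEAE, although all of March is after 14 February |
| 10.11, first dose = first in the study | 1 March | Untreated gap: not a TEAE, listed only |
| 10.11, first dose = Period 2 first dose | 26 March | Period 2 TEAE |

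**How general this is.** Let *g* be the interval in days and *d* the day of the month of Period 2 Day 1. The first of that month falls *g* − (*d* − 1) days after the last Period 1 dose. It lies inside the Period 1 window only if *g* − (*d* − 1) ≤ 30, that is *d* ≥ *g* − 29. Take every start date in a 365-day year against every interval from 56 to 112 days: 365 × 57 = 20,805 combinations.

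- Month overlaps the Period 1 window: possible only for *g* = 56 to 60. The day counts are 53 + 41 + 29 + 18 + 7 = 148, and 148/20,805 = 0.7%. At exactly 56 days it is 53/365 = 14.5%.
- So the month lies wholly after the Period 1 window in 100 − 0.7 = 99.3% of combinations. There the opening rule contradicts the SAP's own Period 1 definition.
- First dose read as first in the study (imputed to the first of the month):
  - *d* = 1 gives a Period 2 TEAE, 12/365 = 3.3%.
  - *d* = 2 puts the event on the admission day, mapped to Period 2 but not treatment-emergent, 12/365 = 3.3%.
  - Period 1 takes 0.7%.
  - The gap takes the rest: (20,805 − 684 − 684 − 148)/20,805 = 92.7%.
- First dose read as the Period 2 first dose: Period 2 TEAE in 100%.

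The percentages weight all combinations equally. They describe how the rules behave, not how often affected records occur.

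**Can both first doses match a partial date?** Not for a month-only date, because the two first doses are at least 4 + 56 = 60 days apart. They can for a year-only date when both doses fall in one calendar year. Section 10.11 then imputes to one or the other without saying which.

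**Effect of one record.** One participant is 100/8 = 12.5 points of Period 1 incidence at n=8 (100/5 = 20 at the minimum of 5), and 100/16 = 6.25 points in Periods 2+3 at about 16 participants. Either shift occurs only if that participant has no other TEAE in the same row.

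**The case against.** The best defence is that the rules can be harmonised. Section 10.11 imputes every partial start date and gives nothing for a wholly missing one. The opening rule of 10.8 could therefore be a residual for undated events, where it agrees with the later sentence. Elsewhere the SAP sets reference dates by period: baseline in 10.1, Study Day 1 in 10.4, emergence in 10.8. Reading first dose the same way gives the Period 2 answer every time. This is probably what was intended. But it must treat the word partial in the opening rule as redundant and supply a period that 10.11 never names. Read literally, 10.11 refers simply to the first dose of treatment.

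The defence is stronger on frequency. The month at issue includes the inpatient stay, with vital signs every 8 hours (Protocol Table B) and an AE query at each assessment (Protocol 8.5.5). Telephone AE reviews are scheduled at Weeks 1 to 4 of Period 3 (Protocol Table C). Time of onset is collected for every AE (Protocol 8.5.4) and missing data are queried (Protocol 10.7). A gap event is still listed, with its original partial date.

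Three stronger readings are tempting but not supported:

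- **That outpatient follow-up, with LTE contacts every 3 months, makes the month-only conflict widespread.** A month after the Period 2 first-dose month is plainly after that dose. The opening rule does not catch it, and Table 2 maps it by its imputed date. Sparse contact bears only on wholly undated events.
- **That the undated default is wrong because Period 1 is a small share of follow-up.** Such a share assumes a constant AE rate, whereas Protocol 2.3.1 says calcium and phosphate fluctuations may be more frequent during initial dose finding. Any default for an undated event is a convention, and this one still counts it as treatment-emergent.
- **That the period counts are in fact misstated.** The documents do not show that any Cohort 1 event has a partial or missing start date.

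**Conclusion.** The point holds for Cohort 1 events whose partial start date spans the Period 2 first dose. For a month-only date, the opening rule of 10.8 gives a period that the SAP's own window excludes in 99.3% of date combinations. The competing rule gives either the gap (92.7%) or Period 2 (100%), depending on an undefined term. This is a minor defect in wording. It probably touches few records and perhaps none, with an effect of at most one participant's share of a row per record. The conclusion rests on the interval running from the last Period 1 dose and on 10.8, 10.11 and 13.6.1 as written. SAP 10.13 and 10.15 were not in the text available, and nothing is inferred from them.

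**What to change.** 1. In SAP 10.8, state that imputation under 10.11 takes precedence for partial dates, and limit the Period 1 default to wholly missing dates.
2. In SAP 10.11, for Cohort 1, where the known month (or year) matches that of a period's first dose, impute to that period's first dose. Month-only events in the Period 2 first-dose month then become Period 2 TEAEs. State which period applies when a year-only date matches both first doses.
3. For wholly undated Cohort 1 events, use the stop date or other record information where it settles the period, and only then apply the Period 1 default. A stop date only caps the onset: it can rule out Period 2 or later but cannot establish it. The contact at which an event was first reported is not among the AE fields listed in Protocol 8.5.4, so the rule should not depend on it.

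The cost is a few sentences and a small programming change; SAP 4.0 allows updates before database lock. Counting Cohort 1 events with partial or missing start dates in the AE listing would show whether any record is affected.
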